## 5.3. Methods to Manage Missing Data

For the analysis of safety endpoints, the sponsor data standard rules for imputation will be applied.

### 5.3.1. Concentrations Below the Limit of Quantification

In all PD data presentations (except listings), concentrations below the limit of quantification (BLQ) will be set to the lower limit of quantification (LLQ).

In all PK data presentations (except listings), concentrations below the limit of quantification (BLQ) will be set to zero.

In listings, BLQ values (for PK, PD, and hsCRP) will be reported as “<LLQ”, where LLQ will be replaced with the value for the LLQ, and BLQ values will be set to LLQ for certain analyses.

### 5.3.2. Deviations, Missing Concentrations and Anomalous Values

For PK and PD summary tables and plots of median profiles, statistics will be calculated having set concentrations to missing if one of the following cases is true:

1. A concentration has been collected as ND (i.e. not done) or NS (i.e. no sample),
2. A deviation in sampling time is of sufficient concern or a concentration has been flagged anomalous by the pharmacokineticist/statistician.

### 5.3.3. Pharmacokinetic Parameters

Actual PK sampling times will be used in the derivation of PK and PD parameters.

If a PK parameter cannot be derived from a participant's concentration data, the parameter will be coded as NC (ie not calculated). (Note that NC values will not be generated beyond the day that a participant discontinues.)

In summary tables, statistics will be calculated by setting NC values to missing, and statistics will be presented for a particular dose with  $\geq 3$  evaluable measurements.

If an individual participant has a known biased estimate of a PK parameter (due for example to an unexpected event such as vomiting before all the compound is adequately absorbed in the body), this will be footnoted in summary tables and will not be included in the calculation of summary statistics or statistical analyses. For PK parameter calculations, the sponsor standard rules will be applied.

### 5.3.4. Multiple Imputation

For summarizing the proportion of responses (e.g. in KCCQ-23 CSS), all change from baseline data from the censored analysis set will be included (i.e. all timepoints up to and including Week 22). A multiple imputation method will be implemented, using a multivariate imputation method by chained equations, which is still valid with an arbitrary missing data pattern. The model will include baseline score and treatment. Additional terms may also be included (eg, cohort, baseline LVEF, log GDF-15 concentration at SV1, baseline log NT-proBNP), as appropriate. Twenty sets of imputations of each missing value will be constructed from the multiple imputation method and the proportion of responses by treatment will be determined with associated standard errors utilizing a normal approximation and will be combined using standard multiple imputation techniques proposed by Rubin to yield overall estimates and CIs. If there is more missing data in the study than anticipated, the number of imputation sets may be increased as required. Note that data for participants who die during the study will be included in the imputation but will then be classed as having a 'Non-response' after imputation.

For logistic regression, all change from baseline data from the censored analysis set will be included (i.e. all timepoints up to and including Week 22). The same imputed datasets as produced for the proportion of responses above will be utilized, where a Logistic Regression model (as described in Section 5.2.4) will be applied to each of the 20 imputed datasets separately. Parameter estimates, of the log odds for each treatment and log odds ratios for each dose relative to placebo, will be combined using standard multiple imputation techniques proposed by Rubin to yield overall estimates of the log odds and log odds ratios and their associated standard errors and will be used to create 90% CIs on the log-odds scale. The log odds (and CIs) and log odds ratios (and CIs) will be back transformed into odds and odds ratios (and CIs) for final reporting.

### 5.3.5. PK Cohort (Cohort B) Participants

For participants in the PK cohort who previously screenfailed from the main cohort, their original screening data (CCI GDF-15, hematology, clinical chemistry, pregnancy test and OL placebo injection for tolerability) will be used if these tests are not repeated at time of rescreening and if rescreening is within 28 days of the original screening.

## 6. ANALYSES AND SUMMARIES

### 6.1. Primary Endpoint(s)

#### 6.1.1. Change from baseline in KCCQ-23 CSS at Week 22 (Cohort A only)

Summaries and analyses will use efficacy approach 1, as described in Section 5.2.

##### 6.1.1.1. Main Analysis

This analysis will be performed on the censored analysis set, as defined in Section 4.

Absolute values and changes from baseline in the KCCQ-23 CSS score will be summarized descriptively by treatment group and timepoint, as described in Section 5.2.1. Tables will include baseline and all post-baseline timepoints.

*Change from baseline in KCCQ-23 CSS at Week 22 will be analyzed using Estimand 1 and an MMRM model, as described in Section 5.2.3. The MMRM model will be fitted to the change from baseline at all post-treatment timepoints up to Week 22 using the Censored analysis set (as defined in Section 4) from Cohort A participants only. Additional terms for baseline LVEF, log CCI GDF-15 concentrations from SV1 and baseline log NT-proBNP will be fitted in the model.*

Additional plots of LS means and differences (including 90% CIs for both), for Week 22 only, will be produced over treatment (for the primary endpoint only).

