4. STUDY DESIGN

4.1. Overall Design

This is a Phase 2, parallel-group, randomized, double-blind, placebo-controlled study to evaluate the effect of ponsegromab on HRQL, physical activity, and circulating biomarkers in adult participants with HF and elevated circulating GDF-15.

For the Main Cohort (Cohort A), Cohort C, and Cohort D, following the 56-day screening period to confirm eligibility, the study will include a 22-week treatment period (from Day 1 to Week 20, and Week 22 for primary endpoint collection), and a 10-week follow-up period for a total study duration of 32 weeks not including the screening period.

Approximately 416 participants will be enrolled into the Main Cohort (Cohort A) and randomized to one of 3 doses of ponsegromab (100 mg [n=18], 200 mg [n=18], or 300 mg [n=190]) or to matched placebo (n=190). Approximately 195 additional participants may be enrolled into optional Cohort C and randomized in a 2:1 ratio to either 100 mg ponsegromab (n~130) or to matched placebo (n~65). The participants in optional Cohort C will allow for a more comprehensive evaluation of the safety and efficacy of the ponsegromab 100 mg dose level compared to placebo. For each of these cohorts, blinded study drug will be administered SC Q4W for a total of 6 doses during the 22-week treatment period.

Participant randomization will be stratified based on CCI

CCI

KCCQ-23 CSS: <45 or ≥45.

The primary endpoint for the study is the change from baseline at Week 22 in KCCQ-23 CSS, an HRQL PRO instrument.

Approximately 100 participants (maximum of approximately 150) who meet all eligibility criteria for Cohorts A and C, except the requirement for serum GDF-15 concentration CCI pg/mL, may be enrolled into the optional Cohort D and randomized in a 1:1 ratio to either 300 mg ponsegromab (n~50) or to matched placebo (n~50), administered SC Q4W for a total

of 6 doses during the 22-week treatment period. Participant randomization in Cohort D will be stratified by KCCQ-23 CSS: <45 or ≥ 45 . The purpose of this optional cohort is for a supportive assessment of efficacy and safety endpoints across the spectrum of GDF-15 concentrations in participants with HF.

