6.3. Assignment to Study Intervention

Allocation of participants to treatment groups in Main Cohort (Cohort A), Cohort C and Cohort D will proceed through the use of an IRT system. The site personnel (study coordinator or specified designee) will be required to enter or select information including but not limited to the user's ID and password, the protocol number, and the participant number. Randomization is stratified based on KCCQ-23 CSS score (Main Cohort [Cohort A], Cohort C and Cohort D) and GDF-15 concentrations (Main Cohort [Cohort A] and Cohort C only) from SV1 assessments; these data points will be required to be entered in the IRT system to ensure appropriate randomization allocations.

The site personnel will then be provided with a randomization number corresponding to the assigned treatment group, and DU or container number(s) when study intervention is being supplied via the IRT system. The IRT system will provide a confirmation report containing the participant number, randomization number, and DU or container number assigned. The confirmation report must be stored in the site's files.

Study intervention will be administered at the study visits summarized in the [SoA](#).

The study-specific IRT reference manual and IPM will provide the contact information and further details on the use of the IRT system.

Open-label, PK cohort (Cohort B): This is an open-label cohort; however, the specific treatment assignment (ie, 100 mg, 200 mg, or 300 mg open-label dose arm) will be assigned using the IRT system. Randomization for this cohort is not stratified.

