#### 4.3. Incorrect Randomization

Participants who are randomized to the wrong stratum, in error, will have the incorrect stratum assignment remain in IMPALA but the clinical database will include the correct stratum. The latter will subsequently be used for all relevant analyses, if appropriate.

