**6.2.3. Change from baseline in 6MWD at Week 22 (Cohorts A and C)**

Summaries and analyses will use efficacy approaches 1 and 3, as described in Section 5.2.

6MWD will be summarized and analyzed across all timepoints, in a similar manner to the main analysis of the primary endpoint, as outlined in Section 6.1.1.1. This analysis will

estimate the treatment effect related to Estimand 4 (as described in Section 2.2.4). Note that for efficacy approach 3, cohort will be included as a term in the statistical model.

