#### Example SAS code for ANCOVA:

NOTE: cohort will be included only when data from more than one cohort are included.

```

proc mixed data=dataset;
  class treatment;
  model cfb = treatment cohort LVEF lgGDF15 lgBNP base / residual
          outp=resid_out;
  lsmeans treatment / diff cl alpha=0.1;
  ods output lsmeans=lsmeans_out;
  ods output diffs=diffs_out;
run;

```

Example SAS code for Logistic Regression Model (without multiple imputation):

Note: the dataset should be ordered with 'Resp'=1 first to ensure that the odds ratios are for a response = 1 and the reference group is Placebo.

NOTE: cohort will be included only when data from more than one cohort are included.

```
* Fit logistic regression;
proc sort data=dataset; by treatment descending resp; run;

proc genmod data= dataset order=internal descending;
  class resp treatment;
  model resp = treatment cohort LVEF lgGDF15 lgBNP
    / dist=bin link=logit alpha=0.1;
  lsmeans treatment / cl diff alpha=0.1 exp;
  ods output lsmeans=odds diffs=oddsrat;
run;

*Odds ratios;
data oddsrat;
  set oddsrat (where=( _TREATTXT="Placebo" ));
  if TREATTXT = ' Ponsegromab 100 mg ' then treatment = 100;
  if TREATTXT = ' Ponsegromab 200 mg ' then treatment = 200;
  if TREATTXT = ' Ponsegromab 300 mg ' then treatment = 300;
  if treatment = . then delete;
  SE = StdErr;
run;
proc sort data=oddsrat; by treatment; run;

data oddsrat;
  set oddsrat;
  oddsratio = exp(estimate);
  LCLoddsratio = exp(LCLMean);
  UCLoddsratio = exp(UCLMean);
run;

* Odds;
data odds;
set odds;
  if TREATTXT = 'Placebo' then treatment = 0;
  if TREATTXT = 'Ponsegromab 100 mg ' then treatment = 100;
  if TREATTXT = 'Ponsegromab 200 mg ' then treatment = 200;
  if TREATTXT = 'Ponsegromab 300 mg ' then treatment = 300;
  if treatment = . then delete;
  SE = StdErr;
run;
proc sort data=odds; by treatment; run;

data odds;
  set odds;
  odds = exp(estimate);
  LCLodds = exp(LCLMean);
  UCLodds = exp(UCLMean);
run;
```

Example SAS code for Cumulative Incidence Plots:

```
proc lifetest data = dataset method=km plots=cif outcif=cifatrisk
intervals=0 to 20 by 4, 22;
  strata trt;
  time day*censor(1) / eventcode=0;
run;
```

NOTE: the censor variable has a value = 1 when the related time is censored and has a value = 0 when the event of interest occurs. There should be no other values available for this censored variable in this dataset (including missing values). If required, missing observations should be removed prior to analysis.

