Example SAS code for Cox Proportional Hazards Model:

To obtain the hazard ratio and 90% CI use SAS proc phreg:

```
proc phreg data=dataset;
  class trt (ref='Placebo') / param=ref order=internal;
  model time*censor(1)= cohort LVEF lgGDF15 lgBNP KCCQ trt / ties=Breslow
    risklimits alpha=0.1;
  hazardratio 'Comparisons vs Placebo' trt / diff=ref alpha=0.1;
run;
```

NOTE: cohort will be included only when data from more than one cohort are included).

Example SAS code for Win-Ratio:

```
* alpha for 100*(1-alpha)% confidence interval;
%let alpha = 0.10;

* number of patients (sample size) in Treatment group;
%let n_trt = 10;

* number of patients (sample size) in Control group;
%let n_con = 10;

data trt;
  set HFdata;
  if treatment = "Ponsegromab";
  rename subject_ID = subid_trt cardio_death=death_trt t_death=t1_trt
    HF_event=HF_trt t_HF=t2_trt CFB_KCCQ=KCCQ_trt;
run;
```

```

data ctrl;
  set HFdata;
  if treatment = "Placebo";
  rename subject_ID = subid_ctrl treatment=control
          cardio_death=death_ctrl t_death=t1_ctrl
          HF_event=HF_ctrl t_HF=t2_ctrl CFB_KCCQ=KCCQ_ctrl;
run;

**** Determine winner in each pair of treatment vs placebo patients ****;

proc sql;
  create table pwdata as
  select a.*, b.*
  from trt as a, ctrl as b
  order by subid_trt, subid_ctrl;
quit;

data compare;
  set pwdata;
  by subid_trt subid_ctrl;

  * win=0: winner not determined, win=1: winner determined or tie;
  win = 0;

  * wincat: winning category;
  * wincat='a','c','e','g' if Control patient won per Endpoint time to
  cardiovascular death, number of worsening HF events, time to 1st
  worsening HF event, CFB in KCCQ-23 at week 22, respectively;
  * wincat='b','d','f','h' if Treatment patient won per Endpoint time to
  cardiovascular death, number of worsening HF events, time to 1st
  worsening HF event, CFB in KCCQ-23 at week 22, respectively;
  * wincat='t' if a pair of patients are tied;
  wincat = ' ';

  if death_trt = 1 then do;
    if death_ctrl = 0 then wincat='a';
    * Control patient won per time to cardiovascular death;
    else if death_ctrl = 1 and t1_trt < t1_ctrl then wincat = 'a';
    * Control patient won per time to cardiovascular death;
    else if death_ctrl = 1 and t1_trt > t1_ctrl then wincat = 'b';
    * Treatment patient won per time to cardiovascular death;
    else if HF_trt > HF_ctrl then wincat = 'c';
    * Control patient won per number of worsening HF events;
    else if HF_trt < HF_ctrl then wincat = 'd';

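### Free improvement: KCCQ-23 CSS is a stratification factor, but the MMRM and ANCOVA models for non-KCCQ endpoints contain no KCCQ term; adding one removes slight conservatism, and the HF-composite logistic model should match its Cox model

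*SAP*

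**What the plan says.** Protocol 6.3: "Randomization is stratified based on KCCQ-23 CSS score (Main Cohort [Cohort A], Cohort C and Cohort D) and GDF-15 concentrations", the latter in Cohorts A and C only, both taken from SV1. Protocol 4.1 gives the cut-point as "KCCQ-23 CSS: <45 or ≥45". In Cohort D, KCCQ is the only stratification factor.

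SAP 6.1.1.1 fixes three covariates for the primary model beyond treatment, time and baseline: "Additional terms for baseline LVEF, log CCI GDF-15 concentrations from SV1 and baseline log NT-proBNP will be fitted in the model". There, baseline is Day 1 KCCQ-23 CSS.

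SAP 6.2.3: "6MWD will be summarized and analyzed across all timepoints, in a similar manner to the main analysis of the primary endpoint". Sections 6.2.4, 6.3.3, 6.3.4 and 6.3.7, the NT-proBNP model in 6.3.12 and the fold-change model in 6.3.13 follow the same pattern. Accelerometry (6.3.8) and hsCRP, albumin and pre-albumin (6.3.12) use the ANCOVA of 5.2.5 with the same added covariates. In all of these, baseline means the endpoint's own baseline. The MMRM and ANCOVA code in Appendix 4 contains no KCCQ variable.

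The HF composite is modelled twice. The logistic code in Appendix 4 (without multiple imputation) reads "model resp = treatment cohort LVEF lgGDF15 lgBNP". The Cox code reads "model time*censor(1)= cohort LVEF lgGDF15 lgBNP KCCQ trt / ties=Breslow", and SAP 5.2.8 lists baseline KCCQ-23 CSS among its possible terms.

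On participants randomised in the wrong stratum, SAP 4.3 says of the correct stratum: "The latter will subsequently be used for all relevant analyses, if appropriate". No listed model contains a stratum variable.

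**The concern.** Stratified allocation balances the arms on the factor, so that factor's share of the outcome variance no longer contributes to the sampling error of the treatment difference. A linear model that omits the factor still counts that share as residual noise. Its standard error is then larger than the true one, its intervals over-cover, and its test runs below the stated level.

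KCCQ-23 CSS could plausibly relate to 6MWD and PROMIS Fatigue. It covers physical limitation and symptoms, and KCCQ fatigue items and the physical limitation score are among the routes to eligibility under inclusion criterion 5. Both endpoints are secondary and tested at one-sided 5% (SAP 5.1). At Interim Analysis #1, the 6MWD, NT-proBNP, hsCRP and HF-composite results also feed predictive probabilities (SAP 7.2.1.1).

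The plan is also uneven. It carries one stratification factor into these models and not the other, and it adjusts the same HF composite for KCCQ in the Cox model but not in the logistic model, without giving a reason.

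**Working it through.** **The plan's own figure.** Protocol 9.5 randomises 190 per arm to 300 mg and placebo in Cohort A and assumes 15% discontinuation: 190 × 0.85 = 161.5, which matches the stated 161 or so evaluable per arm. The effect size, SD and power are redacted, and the documents give no standard error for these models.

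**Inputs.** One-sided level 5%, so z = 1.645, consistent with the 90% intervals (SAP 5.1, 5.2.3). N = 380 for 300 mg plus placebo (Protocol 9.5). Partial R² of the KCCQ stratum given the other covariates, r: not in the documents, so a range is assumed.

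**Linear models.** Omitting the stratum multiplies the reported standard error by 1/√(1 − r), while the true standard error under stratified allocation is unchanged.

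- Interval width ratio = 1/√(1 − r)
- Actual one-sided error = 1 − Φ(1.645/√(1 − r))
- Actual coverage of the 90% interval = 2Φ(1.645/√(1 − r)) − 1

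| r (assumed) | Width ratio | One-sided error | Coverage |
|---|---|---|---|
| 1% | 1.005 | 4.9% | 90.2% |
| 2% | 1.010 | 4.8% | 90.3% |
| 5% | 1.026 | 4.6% | 90.9% |
| 10% | 1.054 | 4.1% | 91.7% |

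**Simulation check.** Permuted blocks of four within strata, 161 per arm, an assumed 60:40 stratum split and 8,000 runs. At r = 2%, 5% and 10%, one-sided error without the stratum was 4.7%, 4.5% and 4.1%; with it, 4.9%, 5.0% and 5.1%. The ratios of reported standard errors were 1.010, 1.026 and 1.054.

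**Power.** Take a test with nominal power of 80% before the gain from stratification (z = 0.842; assumed).

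- Without the term, power = Φ(0.842/√(1 − r)): 80.6% at r = 5% and 81.2% at r = 10%.
- With the term, power = Φ(2.486/√(1 − r) − 1.645): 81.8% and 83.5%.
- The loss is about 1.2 and 2.3 points.
- Equivalent sample-size factor: [(1.645 + z with)/(1.645 + z without)]² = 1.034 and 1.072. Then 380 × (1 − 1/factor) is about 12.6 and 25.4, so roughly 12 to 26 patients.

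If 80% is instead fixed for the adjusted model, the unadjusted model has 78.8% and 77.4%, a loss of 1.2 and 2.6 points.

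**Logistic model for the HF composite.** Simulated with 190 per arm and 3,000 runs. Assumptions: event risk of 10% or 20% in the lower-risk stratum, 40% of patients in the higher-risk stratum, and stratum odds ratio of 1.5 to 3. The standard error of the log odds ratio without the stratum is 0.967 to 0.997 of that with it, so adding KCCQ enlarges it slightly. At a true odds ratio of 0.5, the mean log odds ratio is −0.67 to −0.71 without the term and −0.70 to −0.72 with it. Power rises by 0.1 to 1.1 points. The gain comes from less attenuation, not from a narrower interval.

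**The case against.** The strongest reply is that the effect is small, conservative and rests on an unknown. The relevant quantity is what a KCCQ split at 45 explains in patients already restricted to screening CSS below 75, after the endpoint's own baseline, LVEF, log GDF-15 and log NT-proBNP. A partial R² of 10% means a partial correlation of about 0.32. At 2% the effect is negligible, and for some endpoints it may be zero. Type I error is not inflated, and for most exploratory endpoints SAP 5.1 plans no formal test. All of this stands; it limits the size of the point, not its existence.

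A second reply is that SAP 5.2.3, 5.2.5 and 5.2.6 allow further covariates at discretion, that their lists are only examples, and that the Appendix 4 code is a guide. That is permission rather than prespecification. Section 6.1.1.1 fixes a set of terms without KCCQ, and the other endpoints inherit it. SAP 4.3 is itself qualified, so the missing stratum variable is a gap to close rather than a contradiction.

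Four stronger readings are tempting, and the documents do not support them:

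- *The primary analysis is at fault.* It already adjusts for Day 1 KCCQ-23 CSS and log GDF-15, so both stratification variables are represented. Adding the SV1 score would be an optional refinement whose gain depends on correlations that the documents do not give.
- *The logistic interval is too wide and KCCQ would narrow it.* That is linear-model reasoning; the simulation shows the opposite for the log odds ratio.
- *Adjustment is worth R² × 380, or 19 to 38 patients.* That counts precision which stratified allocation already delivers; only the reported standard error misses it.
- *The win ratio should be stratified too.* No harm from the unstratified all-pairs comparison is shown, and the change would need new code and a choice of weights.

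**Conclusion.** The omission is real and the remedy is free. The linear models for non-KCCQ endpoints drop one of the two stratification factors. Where that factor is prognostic, their intervals are slightly conservative: about 1.0% to 5.4% too wide, with one-sided error of about 4.8% down to 4.1–4.2%, for an assumed partial R² of 2% to 10%. At 5–10% the power cost is about 1.2 to 2.3 points. Every magnitude depends on that assumed R², and the effect vanishes where KCCQ adds nothing.

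The logistic and Cox models for the HF composite are adjusted differently without a stated reason. Aligning them gives a less attenuated odds ratio and about 0.1 to 1.1 points of power under the assumed event rates.

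Only 6MWD and PROMIS Fatigue are secondary endpoints; the rest are exploratory. No finding on the primary endpoint depends on this point.

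**What to change.** In SAP 5.2.3, 5.2.5, 6.2.3, 6.2.4, 6.3.3, 6.3.4, 6.3.7, 6.3.8, 6.3.12 and 6.3.13, and in the MMRM and ANCOVA code of Appendix 4, name KCCQ-23 CSS as a fixed term in every efficacy model whose endpoint is not a KCCQ score. Use either the SV1 value or the stratum split at 45, choose one form for all models, and state that the value corrected under SAP 4.3 is the one fitted.

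In SAP 5.2.6 and its code, add baseline KCCQ-23 CSS to the HF-composite logistic model so that it matches the Cox model.

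Leave the primary model and the win ratio as they are.

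Cost: one term and one degree of freedom per model and a few lines of SAP text and code. No new data are needed, because KCCQ is collected at SV1 and on Day 1 in Cohorts A, C and D. The choice follows from the design, so it can be fixed without reference to results.
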